## 9. MEASUREMENT OF EFFECT

### 9.1 Treatment Efficacy

For the purposes of this study, participants should be re-evaluated for response every 6 weeks. Response and progression will be evaluated in this study using the new international criteria proposed by the Response Evaluation Criteria in Solid Tumors (RECIST) (Eisenhauer et al., 2009). Changes in the diameter (unidimensional measurement) of the tumor lesions are used in the RECIST criteria.

#### 9.1.1 Disease Parameters

**Measurable disease.** Measurable disease is the presence of at least one (1) lesion that can be accurately measured in at least one dimension with longest diameter  $\geq 20$  millimeters (mm) using conventional techniques (CT, MRI, x-ray) or  $\geq 10$  mm with spiral CT scan. Measurable lesions must be at least 2 times the slice thickness in mm. All tumor measurements must be recorded in millimeters (or decimal fractions of centimeters).

**Reminder:** A lesion in a previously irradiated area is not eligible for measurable disease unless there is objective evidence of progression of the lesion prior to study enrollment. Lesions in previously irradiated areas must be clearly identified as such.

**Malignant lymph nodes.** To be considered pathologically enlarged and measurable, a lymph node must be  $\geq 15$  mm in short axis when assessed by CT scan (CT scan slice thickness recommended to be no greater than 5 mm). At baseline and in follow-up, only the short axis will be measured and followed.

**Non-measurable disease.**

All other lesions (or sites of disease), including small lesions (longest diameter  $< 10$  mm or pathological lymph nodes with  $\geq 10$  to  $< 15$  mm short axis, are considered non-measurable disease. Bone lesions, leptomeningeal disease, ascites, pleural/pericardial effusions, lymphangitis cutis/pulmonis, inflammatory breast disease, abdominal masses identified by physical exam that are not measurable by reproducible imaging techniques, and cystic lesions are all considered non-measurable.

Target lesions.

All measurable lesions up to a maximum of 2 lesions per organ and 5 lesions in total, representative of all involved organs, should be identified as target lesions and recorded and measured at baseline. Lesions must be accurately measured in 1 dimension with a minimum size of 10 mm by CT or MRI (slice thickness no greater than 5 mm), 20 mm by *chest* x-ray. Nodes must have a short axis  $\geq 15$  mm. The short axis should be included in the sum of the lesions in the calculation of response. Nodes that shrink to  $< 10$  mm are considered normal. Target lesions should be selected on the basis of their size, be representative of all the involved organs, and should be lesions that can be followed with reproducible repeated measurements.

Lytic bone lesions or mixed lytic-blastic lesions, *with identifiable soft tissue components*, that can be evaluated by cross sectional imaging techniques such as CT or MRI can be considered target lesions if the *soft tissue component* meets the definition of measurability as defined above. Cystic lesions thought to represent cystic metastases can be considered as target lesions. However, if non-cystic lesions are present, these are preferred for selection as target lesions. Lesions in previously irradiated areas or areas subject to other loco-regional therapy are usually not considered measurable unless there has been demonstrated progression of that lesion.

Non-target lesions.

All other lesions, including small lesions  $< 10$  mm or pathological lymph nodes measuring  $\geq 10$  mm to  $< 15$  mm in short axis, as well as truly non-measurable lesions, which include leptomeningeal disease, ascites, pleural or pericardial effusion, inflammatory breast disease, lymphangitic involvement of skin or lung, abdominal masses identified by physical exam that are not measurable by reproducible imaging techniques.

### 9.1.2 Methods for Evaluation of Measurable Disease

The same method of assessment (CT or MRI) and the same technique should be used to characterize each identified and reported lesion at baseline and during follow-up. Spiral CT should be performed using a 5 mm contiguous reconstruction algorithm.

### 9.1.3 Response Criteria

#### 9.1.3.1 Evaluation of Target Lesions

Complete Response (CR):

Disappearance of all target lesions. Any pathological lymph node must have reduction in short axis to  $< 10$  mm.

Partial Response (PR):

At least a 30% decrease in the sum of the diameters of target lesions, taking as reference the baseline sum diameters.

Progressive Disease (PD):

At least a 20% increase in the sum of the diameters of target lesions, taking as reference the smallest sum on study with at least a 5 mm absolute increase in the sum of all lesions. The appearance of one or more new lesions\* denotes disease progression.

Stable Disease (SD):

Neither sufficient shrinkage to qualify for PR nor sufficient increase to qualify for PD, taking as reference the smallest sum diameters while on study.

Unknown (UN): Assessment of target lesions cannot be made due to insufficient or unevaluable data. In this case, a concise explanation must be given.

**Note:** If tumor response data is missing for target lesions, the overall assessment must be UN unless there is new disease that would result in an overall assessment of PD. However, if there is missing or unevaluable data for non-target lesions, but data is available for all target lesions, the overall response for that time point will be assigned based on the sum LD of all target lesions. Additionally, the assessment of CR cannot be made if there is missing or unevaluable data for non-target lesions. In this case, the overall assessment would be PR.

**\*Definition of New Lesion:** The finding of a new lesion should be unequivocal (i.e. not due to difference in scanning technique, imaging modality, or findings thought to represent something other than tumor (ex: new bone lesions may be healing or flare of pre-existing lesions). However, a lesion identified on a follow-up scan in an anatomical location that was not scanned at baseline is considered new and will indicate PD. If a new lesion is equivocal (because of small size, etc.), follow-up evaluation will clarify if it truly represents new disease and if PD is confirmed, progression should be declared using the date of the initial scan on which the lesion was discovered.

#### 9.1.3.2 Evaluation of Non-Target Lesions

Complete Response (CR): Disappearance of all non-target lesions. All lymph nodes must be non-pathological in size (< 10 mm short axis).

Incomplete Response/Stable Disease (SD): Persistence of one or more non-target lesions.

**Progressive Disease (PD):** Appearance of one or more new lesions\* (new lesions must be > slice thickness) and/or unequivocal progression of existing non-target lesions and /or overall level of substantial worsening that merits discontinuation of therapy. A useful test that can be applied when assessing non-targets for unequivocal progression is to consider if the increase in overall disease burden based on the change in non-measurable disease is comparable in magnitude to the increase that would be required to declare PD for measurable disease.

**Unknown (UN):** Assessment of non-target lesions cannot be made due to insufficient or unevaluable data. In this case, a concise explanation must be given.

**\*Definition of New Lesion:** The finding of a new lesion should be unequivocal (i.e. not due to difference in scanning technique, imaging modality, or findings thought to represent something other than tumor (ex: new bone lesions may be healing or flare of pre-existing lesions). However, a lesion identified on a follow-up scan in an anatomical location that was not scanned at baseline is considered new and will indicate PD. If a new lesion is equivocal (because of small size, etc.), follow-up evaluation will clarify if it truly represents new disease and if PD is confirmed, progression should be declared using the date of the initial scan on which the lesion was discovered.

#### 9.1.3.3 Evaluation of Best Overall Response

The best overall response is the best response recorded from the start of the treatment until disease progression/recurrence (taking as reference for progressive disease the smallest measurements recorded since the treatment started). The participant's best response assignment will depend on the achievement of both measurement and confirmation criteria.

**Table 7. Evaluation of Best Overall Response**

| Target Lesions | Non-Target Lesions          | New Lesions | Overall Response | Best Overall Response for when Confirmation is Required: |
|----------------|-----------------------------|-------------|------------------|--|
| CR             | CR                          | No          | CR               | $\geq 4$ wks confirmation                                |
| CR             | Non-CR/Non-PD               | No          | PR               |  |
| CR             | Not evaluated               | No          | PR               | $\geq 4$ wks confirmation                                |
| PR             | Non-CR/Non-PD/Not evaluated | No          | PR               |  |
| SD             | Non-CR/Non-PD/Not evaluated | No          | SD               | Documented at least once $\geq 4$ wks from baseline      |
| PD             | Any                         | Yes or No   | PD               | No prior SD, PR or CR                                    |
| Any            | PD*                         | Yes or No   | PD               |  |
| Any            | Any                         | Yes         | PD               |  |

\* In exceptional circumstances, unequivocal progression in non-target lesions may be accepted as disease progression.

**Note:** Participants with a global deterioration of health status requiring discontinuation of treatment without objective evidence of disease progression at that time should be reported as "*symptomatic deterioration*". Every effort should be made to document the objective progression even after discontinuation of treatment.

#### 9.1.4 Duration of Response

**Duration of overall response:** The duration of overall response is measured from the time measurement criteria are met for CR or PR (whichever is first recorded) until the first date that recurrence or PD is objectively documented, taking as reference for PD the smallest measurements recorded since the treatment started.

**Duration of overall complete response:** The duration of overall CR is measured from the time measurement criteria are first met for CR until the first date that recurrent disease is objectively documented.

**Duration of stable disease:** Stable disease is measured from the start of the treatment until the criteria for progression are met, taking as reference the smallest measurements recorded since the treatment started.

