| Survival   |                |         |   |   |         |    |   |                   |    |                 |                  |                     | X                     | X                         | X            |     |
| Tumor sample for mutation and amplification testing  | X              |         |   |   |         |    |   |                   |    |                 |                  |                     | X                     | X                         | X            |     |

1. Vital signs – During treatment period, vital signs will be performed pre-dose (including temperature, respiratory rate, blood pressure, pulse, weight and ECOG PS) and immediately post-dose infusion (including temperature, respiratory rate, blood pressure and pulse).
2. ECG- Please refer to Table 3 for detailed schedule of ECGs.
3. In women of child-bearing potential, a serum pregnancy test must be obtained prior (within 14 days) to the first administration of AUY922. CHEMISTRY: BUN, Creatinine, Glucose, Total Protein, Albumin, AST/SGOT, ALT/SGPT, Total Bilirubin, Alkaline Phosphatase, Magnesium, Calcium, Sodium, Potassium, Phosphorous. HEMATOLOGY: CBC with differential
4. Standard ophthalmologic assessments will be required at baseline and follow-up exams will be conducted at the time when visual symptoms are reported (if any), at cycle 3 day 1 if no visual symptoms are reported, and at study discontinuation. There is a +/- 7 day window allowed for eye exam at Cycle 3 day 1
5. One should aim to administer AUY922 on the same day each week, but there is a +/- 2 day window allowed to account for holidays, inclement weather, transportation difficulties, etc. For patients who are unable to tolerate the protocol-specified dosing schedule, schedule adjustments are permitted. This includes the ability to skip a week of dosing if needed up to once per cycle. Patients who continue treatment beyond progression can skip up to two infusions per cycle if needed after discussion between the treating MD and the overall PI of the study.
6. A CT scan with contrast of the chest, abdomen, and pelvis will be performed on patients at baseline (screening) -30 to -1 days prior to study drug administration. The same type of imaging modality (CT with contrast or MRI) used at screening must be used for all subsequent follow-up assessments. Follow-up CT/MRI scans will be performed every 6 weeks ( $\pm$ 7 days) from registration.

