7. In the event that a patient is discontinued from treatment for any reason other than disease progression, an end of treatment CT/MRI is recommended to be performed if the last scan was conducted  $\geq$  4 weeks previously. Such patients who discontinue study treatment for reasons other than disease progression should be re-staged every 12 weeks ( $\pm$ 7 days) until start of another anti-cancer treatment.
8. Patients will be followed for survival every 3 months after discontinuing the trial. Follow-ups may be conducted over the telephone.
9. If available, tumor samples will be sequenced for EGFR exon 20 mutation.
10. For patients who miss a D1 visit of any cycle (as allowed per protocol,) any missed day 1 assessments (for example, coagulation studies and urinalysis) will be performed at the next clinic visit.

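### Stable disease of at least 3 months decides both stages, yet a patient who stops drug soon after week 6 without progression may next be scanned at about week 18, so an earlier progression can score as a success

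*Combined protocol and SAP*

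**What the plan says.** Sections 1.1, 13.1 and 13.2 let response or SD of at least 3 months decide the trial. No success in the first 10 patients stops it, and 4 or more in 29 supports further evaluation. Section 13.2 sets the null rate of this combined endpoint at 5% and the target at 20%. Section 13.6 makes all patients evaluable, so early stoppers count.

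On duration, Section 9.1.4 says "Stable disease is measured from the start of the treatment until the criteria for progression are met". Table 7 accepts SD as best response once it has been documented a single time, at least 4 weeks from baseline.

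On scans:
- Section 9.1: "participants should be re-evaluated for response every 6 weeks".
- Study calendar (Table 6), footnote 6: "Follow-up CT/MRI scans will be performed every 6 weeks", within 7 days either way, counted from registration.
- Footnote 7, for patients who stop for a reason other than progression: "an end of treatment CT/MRI is recommended to be performed if the last scan was conducted" at least 4 weeks before. Then: "Such patients who discontinue study treatment for reasons other than disease progression should be re-staged every 12 weeks", again within 7 days, "until start of another anti-cancer treatment".

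The note to Table 7 foresees "Participants with a global deterioration of health status requiring discontinuation of treatment without objective evidence of disease progression at that time" and adds: "Every effort should be made to document the objective progression even after discontinuation of treatment".

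I found no text that converts 3 months to days, requires a progression-free scan at that time, or says how death, new therapy or a missing scan is scored for SD duration. By contrast, Section 13.7 does count death as an event for progression-free survival.

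**The concern.** SD has a start date and one way to end: documented progression. If nobody looks between week 6 and about week 18, a progression at week 8 is dated at about week 18, and the patient passes the 3-month test without having been stable for 3 months. If another treatment starts first, scheduled re-staging ends and SD may have no end date.

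The thresholds are low enough for single patients to matter. One such patient among the first 10 opens stage 2 alone. The opposite error is also possible: with no written rule, an analyst could close SD at the last scan and fail a patient who was truly stable. Either way, the result could turn on a choice made after the data are seen.

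**Working it through.** **1. The plan's own figures.** Section 13.2 gives 10 patients in stage 1 (stop at 0 successes), 19 more in stage 2, and a go at 4 or more of 29.

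P(go) = Σ over x = 1 to 10 of P[Bin(10, p) = x] × P[Bin(19, p) ≥ 4 − x].

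- p = 0.05: 0.0468 (stated 0.047).
- p = 0.20: 0.8011, so beta is 0.199 (stated 0.199).
- Stopping after stage 1 at p = 0.05: 0.95^10 = 0.599.

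The Simon arithmetic is right.

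**2. The calendar.** I take 3 months as 91 days (13 weeks), which the documents do not define, and registration as close to the first dose.

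- The week-6 scan shows SD, which is enough for Table 7.
- Drug stops before week 6 + 4 = week 10, without progression. The last scan is under 4 weeks old, so footnote 7 recommends no end-of-treatment scan.
- Next scheduled scan: week 6 + 12 = week 18 (day 126) if the interval runs from the last scan. If it runs from the stop date, it can be as late as about week 22.
- Earliest case, both windows used: week 5 + 11 = week 16 = day 112, still 21 days past day 91.

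Progression at week 8 is therefore first seen, on schedule, after 3 months.

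**3. One or two wrongly scored patients.** Place them at random among the 29 and let the others succeed at 5%.

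- One, in stage 1 (weight 10/29): 3 or more of the other 28 are needed, P = 0.163. In stage 2 (19/29): the same, plus at least one success among the first 10, P = 0.128. Weighted: **0.140**.
- Two, both in stage 2 (weight (19×18)/(29×28) = 0.421): 2 or more of the other 27 and at least one success among the first 10, P = 0.270. At least one in stage 1 (weight 0.579): 2 or more of 27, P = 0.394. Weighted: **0.342**.

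These figures are conditional on the errors having occurred.

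**4. Illustration by frequency (assumptions not in the documents).** Assume exponential time to progression, 5% progression-free at day 91, and the whole 5% made up of SD. The fraction progression-free at day 42 is then 0.05^(42/91) = 0.251. Let s be the share of *those* patients who stop then and are not scanned until about week 18. The scored rate is (1 − s) × 0.05 + s × 0.251.

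| s | scored rate | P(go) |
|---|---|---|
| 5% | 6.0% | 0.080 |
| 10% | 7.0% | 0.123 |
| 20% | 9.0% | 0.230 |

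Unscheduled scans lower these figures. If half of the stoppers are scanned in time, they become 0.062, 0.080 and 0.123.

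**The case against.** **Other text reaches these patients.** The note to Table 7 asks for effort to document progression after stopping. Section 9.1.3.2 counts, for non-target disease, substantial overall worsening that justifies stopping therapy as progression, so some patients who stop for deterioration may already qualify. Section 9.1.3.1 makes a time point with missing target-lesion data unknown. All of this stands and softens the gap. None of it closes it: the first sets no date, the second does not reach a patient who stops for toxicity, and the third does not say when SD ends.

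**The route needs several events together.** It takes SD at week 6, a stop before about week 10 without progression, progression before 3 months, and no unscheduled scan. That is fair, and it is why no frequency can be claimed.

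**Section 9.1 already requires 6-weekly evaluation.** A reader might infer a contradiction with footnote 7. The two read naturally as a general rule and a specific exception, so I do not call it one. The plan should still say which interval serves this endpoint.

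**A week-12 landmark is an easier endpoint.** Day 84 falls 7 days short of day 91. This stands: the stated error rates carry over only if the plan says that 5% and 20% are rates of the endpoint so defined. A scan at or after a defined 3-month day would keep the present endpoint, but the 6-week schedule has no scan there before week 18.

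**Conclusion.** The gap is real and follows from the plan's own schedule: progression well before 3 months can be recorded as SD of at least 3 months in a patient who stopped drug early. Its frequency is unknown. P(go) at the 5% null rate rises from 0.047 to 0.140 given one wrongly scored patient and to 0.342 given two. The values 0.080, 0.123 and 0.230 are illustrations under assumed shares and an exponential model.

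Three stronger readings are tempting but not supported:

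- *The true type I error is 0.14 or 0.34.* Those figures assume that the errors have happened; they are not the design's alpha.
- *The 5%, 10% and 20% are shares of all patients, or the results are upper bounds.* They are shares of patients progression-free at week 6, about 25% of the total in the model. As shares of all patients they would give 0.23, 0.48 and 0.83, but 20% of all patients would be about 80% (0.20/0.251) of those progression-free at week 6.
- *Patients still on drug have the same problem because the week-12 scan falls just before 3 months.* That matters only if the 5% null is a rate in true time rather than one measured on this scan schedule. The documents do not say which.

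**What to change.** In Sections 9.1.4 and 13.2, with 1.1 and 13.1 referring to them:

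1. SD of at least 3 months requires a RECIST assessment without progression at the protocol's 3-month assessment, on or off drug. Name it in days from cycle 1 day 1: the week-12 scan (day 84) of the existing 6-week schedule, with its window.
2. Progression first documented at a later scan does not count as SD of 3 months when there is no progression-free assessment at that time point.
3. Progression, death or new anti-cancer therapy before that assessment, or a missing assessment, is a non-success in the primary analysis. A sensitivity analysis uses the next available scan for missing assessments. CR and PR count as now.
4. State that 5% and 20% are rates of this endpoint.
5. State in Section 9.1 and footnote 7 which scan interval applies to this endpoint after stopping without progression.

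The cost is wording; the 10 + 19 patients stay. The stated 0.047 and 0.801 hold if no true success lacks the scan. If 10% or 20% do, the rate under the target falls to 0.20 × 0.9 = 18% or 0.20 × 0.8 = 16%, and power to 0.73 or 0.64. The null rate falls to 4.5% or 4.0%, and alpha to 0.034 or 0.023. Keeping the week-12 scan for patients off drug without progression avoids most of this loss, at one extra scan per early stopper.

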#### 9.1.5 Progression-Free Survival

Progression-Free Survival (PFS) is defined as the duration of time from start of treatment to time of objective disease progression.

### 9.1.6 Response Review

Restaging imaging will be assessed at the DF/HCC Tumor Imaging Metrics Core to provide unbiased formal RECIST measurements

## 10. ADVERSE EVENT REPORTING REQUIREMENTS

### 10.1 Definitions

#### 10.1.1 Adverse Event (AE)

An adverse event (AE) is any undesirable sign, symptom or medical condition or experience that develops or worsens in severity after starting the first dose of study treatment or any procedure specified in the protocol, even if the event is not considered to be related to the study.

Abnormal laboratory values or diagnostic test results constitute adverse events only if they induce clinical signs or symptoms or require treatment or further diagnostic tests.

